#### **5.3.2.2. Effectiveness (Responder-based): rMenB+OMV NZ - 3 doses (0,2,6-months schedule)**

Not applicable

#### **5.3.2.3. Vaccine effectiveness (Test-based): rMenB+OMV NZ - 2 doses (0,6-months schedule)**

See Section 5.3.2.1, with the difference in the treatment arm:

```
PROC GENMOD data=dataset descending;
class trtgrp strain region agecat previousACWY subject_id ;
model outcome = trtgrp strain region agecat previousACWY / dist= bin
link= log DSCALE ;
repeated subject = subject_id / type= CS withinsubject= strain ;
estimate 'MenB06-ACWY' trtgrp 0 1 0 0 -1/ alpha=0.025 exp;
/*trtgrp S is MenB0,6 and trtgrp W is ACWY*/
run;
```

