## CONFIDENTIAL

205416 [MENB REC 2ND GEN-038 (V72\_72)]  
Statistical Analysis Plan Amendment 4**Table 3 Overview of study design: Vaccination and Blood Draw Schedule**

Visits Study Day	Visit 1 Day 1	Visit 2 Day 31	Visit 3 Day 61	Visit 4 Day 91	Visit 5 Day 181	Visit 6 Day 211
Group MenB_0_2_6 N=912	Pre-vacc Blood sample  rMenB+OMV NZ	Post-vacc 1 Blood sample	rMenB+OMV NZ	Post-vacc 2 Blood sample	rMenB+OMV NZ	Post-vacc 3 Blood sample  MenACWY
Group MenB_0_6 N=912	Pre-vacc Blood sample  rMenB+OMV NZ	Post-vacc 1 Blood sample	MenACWY	Post-vacc 2 Blood sample	rMenB+OMV NZ	Post-vacc 3 Blood sample  Placebo
Group ABCWY-1 N=548	Pre-vacc Blood sample  MenABCWY-1	Post-vacc 1 Blood sample	Placebo	Post-vacc 2 Blood sample	MenABCWY-1	Post-vacc 3 Blood sample  Placebo
Group ABCWY-2 N=548	Pre-vacc Blood sample  MenABCWY-2	Post-vacc 1 Blood sample	Placebo	Post-vacc 2 Blood sample	MenABCWY-2	Post-vacc 3 Blood sample  Placebo
Group ABCWY-3 N=548	Pre-vacc Blood sample  MenABCWY-3	Post-vacc 1 Blood sample	Placebo	Post-vacc 2 Blood sample	MenABCWY-3	Post-vacc 3 Blood sample  Placebo
Group ACWY N=150	Pre-vacc Blood sample  MenACWY	Post-vacc 1 Blood sample	Placebo	Post-vacc 2 Blood sample	rMenB+OMV NZ	Post-vacc 3 Blood sample  rMenB+OMV NZ

N = number of subjects; Pre-vacc = pre-vaccination; Post-vacc = post-vaccination

- Treatment allocation: At Day 1, prior to the study vaccination, subjects will be randomised to 1 of the 6 study groups according to a 5:5:3:3:3:1 ratio.
- Blinding: Observer-blind. Kindly refer to Protocol Section 7.3 for details on blinding and unblinding procedures.
- Sampling schedule:
  - A total of 4 blood samples\* will be collected from each subject at Day 1 (pre-vaccination blood sample; approximately 20 mL), at Day 31 (post-vaccination 1 blood sample; approximately 25 mL), at Day 91 (post-vaccination 2 blood sample; approximately 25 mL) and at Day 211 (post-vaccination-3 blood sample; approximately 25 mL).
  - Urine sampling: Urine samples for pregnancy testing will be collected from female subjects of child-bearing potential at Visit 1 (Day 1), Visit 3 (Day 61), Visit 5 (Day 181) and Visit 6 (Day 211) prior to the vaccination.

\* Insufficient blood volume may lead to test cancellation and jeopardise the statistical power. Hence, every effort must be done to collect blood volume as per protocol requirements.

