#### **5.3.1.1. Vaccine effectiveness (Test-based): rMenB+OMV NZ - 3 doses (0,2,6-months schedule)**

Analysis set: Per-protocol set (PPS) will be the primary analysis population

Statistical method: The VE is defined as  $1 - RR = (1 - \text{percentage of samples without bactericidal serum activity at 1:4 dilution in MenB group} / \text{percentage of samples without bactericidal serum activity at 1:4 dilution in the ACWY group}) \times 100\%$  and it will be analyzed using a generalised linear model with vaccine group, strain, and randomization factors (i.e. region (US/ex-US), age category (10-17 YoA/18-25 YoA), previous MenACWY vaccination (y/n)) as independent variables. Furthermore, a repeated statement will be used to estimate the variance of the RR including correlation within subject's responses to different strains. If the statistical model does not converge due to (one of) the factor(s), a model without this/these factor(s) will be fitted instead. The response variable of the model will be the Bernoulli distributed outcome without bactericidal activity at a 1:4 dilution (i.e. response is 1 if titre  $< 4$ , and 0 if titre  $\geq 4$ ), at 1 month after the last vaccination (Month 7) in the MenB group and at Month 1 for the ACWY group. Each subject will contribute with approximately 35 measures to this analysis, each of the measures corresponding to the response variable to one of the 35 strains randomly assigned to be tested with the samples available for that specific subject.

In order to obtain the VE measure which is a measure based on the relative risk (RR), a generalised linear model will be used with the Binary distribution and link function log in order to compute the log RR and the corresponding 97.5% CI. The obtained values will be exponentiated to obtain the RR and the corresponding 97.5% CI. The VE will be computed as  $100\% \times (1 - RR)$ . Effectiveness of rMenB+OMV NZ (0,2,6-months schedule) will be demonstrated if the lower limit of the two-sided 97.5% CI for VE between MenB and the ACWY group is above 65%.

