#### 5.3.2.1. Vaccine effectiveness (Test-based): rMenB+OMV NZ - 3 doses (0,2,6-months schedule)

The SAS code to analyse the Vaccine effectiveness (Test-based): rMenB+OMV NZ - 3 doses (0,2,6-months schedule) objective is specified below. Treatment, region, age category, previous ACWY vaccination, and strains will be modelled as fixed effect. To account for a possible over-dispersion, the DSCALE option in the model statement will be evaluated first. The DSCALE will be kept in the model only if the F-statistics for the DSCALE parameter is significant ( $p<0.05$ ). The following SAS code will be used for the VE calculation:

```

ods trace on;
ods output GEEmpPEst = genmod_stats
CONVERGENCESTATUS = converge ;

PROC GENMOD data=dataset descending;
class trtgrp strain region agecat previousACWY subject_id ;
model outcome = trtgrp strain region agecat previousACWY / dist= bin
link= log DSCALE;
repeated subject = subject_id / type= CS withinsubject= strain;
estimate 'MenB026-ACWY' trtgrp 1 0 0 0 0 -1/ alpha=0.025 exp;

/*trtgrp R is MenB0,2,6 and trtgrp W is ACWY*/

run;

ods output close;

data genmod_stats;
set genmod_stats;
where parm = 'trtgrp' and level1 = '1';
rr = exp(estimate);
ub = exp(uppercl);
ve = (1 - rr)*100 ;
ve_ll = (1 - ub) * 100 ;
if ve_ll > 65 then success = 1 ;
else success = 0 ;
run;

```

where outcome represents the Bernoulli distributed outcome without bactericidal activity at a 1:4 dilution (i.e. response is 1 if titre  $< 4$ , and 0 if titre  $\geq 4$ ), one month after the 3rd vaccination in MenB 0,2,6 and one month after the MenACWY vaccination for the ACWY arm, trtgrp indicates the vaccine groups, strain is the serogroup B strain variable, region is either US or ex-US, agecat is the age at enrolment (10-17 YoA or 18-25 YoA), and previousACWY is previous ACWY vaccination (y/n) at enrolment.

rr is the relative risk (RR), which is obtained from the estimated parameters from PROC GENMOD. Vaccine effectiveness (VE) is then derived as (1-rr)x100%.

ub represents the upper bound of the 97.5% CI of the relative risk. ve\_ll is the lower bound of the 97.5% CI for VE, if the value is greater than 65%, then the Vaccine effectiveness (Test-based): rMenB+OMV NZ - 3 doses (0,2,6-months schedule) objective is successful.

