### 5.3.2.9. Vaccine effectiveness (Test-based): MenABCWY

See Section 5.3.2.1, with the difference in the estimate statement:

```
PROC GENMOD data=dataset descending;
class trtgrp strain region agecat previousACWY subject_id ;
model outcome = trtgrp strain region agecat previousACWY / dist= bin
link= log DSCALE ;
repeated subject = subject_id / type= CS withinsubject= strain ;
estimate 'MenABCWY-ACWY' trtgrp 0 0 1 1 1 -3/ alpha=0.025 exp
divisor=3;

/*trtgrp T, U, and V are the ABCWY-1, ABCWY-2, and ABCWY-3 lots and
trtgrp W is ACWY*/
run;
```

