#### **5.3.2.3. Vaccine effectiveness (Test-based): rMenB+OMV NZ - 2 doses (0,6-months schedule)**

See Section [5.3.2.1](#), with the difference in the treatment arm:

```
PROC GENMOD data=dataset descending;
class trtgrp strain region agecat previousACWY subject_id ;
model outcome = trtgrp strain region agecat previousACWY / dist= bin
link= log DSCALE ;
repeated subject = subject_id / type= CS withinsubject= strain ;
estimate 'MenB06-ACWY' trtgrp 0 1 0 0 0 -1/ alpha=0.025 exp;
/*trtgrp S is MenB0,6 and trtgrp W is ACWY*/
run;
```

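### In SAP Amendments 2 and 4 the printed contrast for the rMenB 0,6-months schedule has five coefficients for six groups, so it gives ACWY no weight and compares MenB_0_6 with ABCWY-3

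*SAP*

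**What the plan says.** Section 5.3.1.1 defines VE against the ACWY group and declares effectiveness "if the lower limit of the two-sided 97.5% CI for VE between MenB and the ACWY group is above 65" per cent. Section 5.3.1.3 applies the same method to the 0,6-months schedule.

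Section 5.3.2.3 of Amendment 4 refers back to the code in 5.3.2.1 and restates the procedure with a changed contrast: "estimate 'MenB06-ACWY' trtgrp 0 1 0 0 -1/ alpha=0.025 exp". The comment beneath it reads "trtgrp S is MenB0,6 and trtgrp W is ACWY". Amendment 2 prints the same five coefficients. Amendment 3 prints "estimate 'MenB06-ACWY' trtgrp 0 1 0 0 0 -1/ alpha=0.025 exp", and Amendment 1 has the same six coefficients under a different label.

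The number and order of the levels are fixed elsewhere in Amendment 4:

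- Section 3.2, below Table 3: "subjects will be randomised to 1 of the 6 study groups according to a 5:5:3:3:3:1 ratio".
- Section 5.3.2.1, where the comment names R as MenB 0,2,6 and W as ACWY: "estimate 'MenB026-ACWY' trtgrp 1 0 0 0 0 -1/ alpha=0.025 exp".
- Section 5.3.2.9: "estimate 'MenABCWY-ACWY' trtgrp 0 0 1 1 1 -3/ alpha=0.025 exp", with divisor 3. Its comment begins "trtgrp T, U, and V are the ABCWY-1, ABCWY-2, and ABCWY-3 lots and" and goes on to name W as ACWY.

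**The concern.** A contrast in this kind of code is read by position. With one coefficient missing, the negative weight moves from the control arm to the arm before it. The result would be labelled as MenB_0_6 against ACWY, but it would compare two arms that each received two MenB-containing doses at 0 and 6 months.

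The weights still sum to zero, so the statement would be estimable and would run without an error.

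The 0,6-months test-based result is a primary objective in a hierarchy. Under section 6, a non-rejection stops testing before the 0,2-months schedule, blocks the transfer of alpha to the MenABCWY objectives, and makes the 0,2,6-months schedule the non-inferiority comparator.

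**Working it through.** **Level order.** The comments in 5.3.2.1, 5.3.2.3 and 5.3.2.9 give R = MenB_0_2_6, S = MenB_0_6, T, U, V = ABCWY-1, -2, -3, and W = ACWY. Coefficients that are not listed at the end count as zero.

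**Mapping each contrast by position.**

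| Contrast | R | S | T | U | V | W | Result |
|---|---|---|---|---|---|---|---|
| 5.3.2.1, Amendment 4 | 1 | 0 | 0 | 0 | 0 | -1 | R - W, matches label |
| 5.3.2.9, Amendment 4 (divided by 3) | 0 | 1/3 on each of T, U, V: see note | | | | -1 | mean(T, U, V) - W, matches label |
| 5.3.2.3, Amendments 2 and 4 | 0 | 1 | 0 | 0 | -1 | none, so 0 | S - V, does not match label |
| 5.3.2.3, Amendment 3 (and 1) | 0 | 1 | 0 | 0 | 0 | -1 | S - W, the intended comparison |

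Note: in 5.3.2.9 the weights are R = 0, S = 0, T = U = V = 1/3, W = -1.

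The two sibling contrasts come out as labelled, which confirms the level order. The sum for the printed 0,6 contrast is 0 + 1 + 0 + 0 - 1 = 0.

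**Could five coefficients be right?** With the lots kept apart there are six levels; with the lots pooled there are four. Amendment 4 uses the same model statement in all three sections, and only 5.3.2.3 lists five coefficients.

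**Size if VE is read from this statement.** VE = 1 - RR, where RR is the ratio of the percentages of samples without bactericidal activity. The SAP part at hand gives no such percentages, so these are assumptions: ACWY 70% to 95%, MenB_0_6 10% to 20%, ABCWY-3 10% to 20%.

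- Intended contrast (S against W): lowest 1 - 0.20/0.70 = 71.4%; highest 1 - 0.10/0.95 = 89.5%.
- Printed contrast (S against V): lowest 1 - 0.20/0.10 = -100%; highest 1 - 0.10/0.20 = 50%; with equal rates, for example 1 - 0.15/0.15 = 0%.

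Over this range the printed contrast cannot have a lower limit above 65%, because even its point estimate stays at or below 50%. The intended point estimate is above 65% throughout. Whether its lower limit is above 65% depends on the variance, which was not computed.

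**Which output is used.** In 5.3.2.1 the data step that sets the success flag filters the GEE parameter-estimate table for a treatment-group row. It does not read the ESTIMATE result. Section 5.3.2.3 shows no data step of its own. On the other hand, in Amendment 4 the ESTIMATE statement is the only place in this code where alpha is set to 0.025, and it is what 5.3.2.3 changes for the 0,6 schedule. The printed code therefore does not settle which output supplies VE.

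**The case against.** Four objections carry weight.

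1. *Amendment 4 is superseded.* Amendment 5 is the latest version, and its section 5.3.2.3 is outside the part of the SAP reviewed. This stands: the fault is shown for Amendments 2 and 4, not for the plan in force.

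2. *A zero may have been lost in reading the PDF.* The count runs six, five, six, five over Amendments 1 to 4, and the extracted text has other character slips, such as two spellings of the GEE output table name. This cannot be excluded. Against it, the same five-coefficient string appears in two separate amendments, and the longer runs of zeros in 5.3.2.1 and 5.4.2.2 of those amendments are intact. The source PDF will decide.

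3. *The intent is clear.* The label, the comment and sections 5.3.1.1 and 5.3.1.3 all name ACWY as the reference, and a VE near 0% would be conspicuous. This also stands: the estimand and the hypothesis are not misstated. It does not make the printed line correct.

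4. *The success flag does not use this statement.* As shown in the working, that is true of the printed data step.

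A reader might infer that the 0,6 objective would fail, that testing would stop, and that the comparator would default to 0,2,6. The documents do not support that without conditions. It would require the five-coefficient line to be in the operative program, VE to be taken from its output, and killing rates like those assumed.

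**Conclusion.** As printed in section 5.3.2.3 of Amendments 2 and 4, the 0,6-months contrast compares MenB_0_6 with ABCWY-3 and gives ACWY zero weight. That contradicts its label, its comment, the definition of VE in 5.3.1.1, and the form in Amendments 1 and 3. This part rests only on the printed text and the level order, subject to confirmation against the source PDF.

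The consequence is conditional. If VE for the 0,6 schedule comes from this statement, it estimates rMenB against MenABCWY, and the 65% criterion could be wrongly failed. If it comes from the parameter table, as the printed data step has it, this error does not set the decision. The numerical range rests on assumed rates. Because the line belongs to the code for a primary objective and would run without an error, it merits a definite check and correction.

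**What to change.** 1. Check the coefficient string in the source PDF, in section 5.3.2.3 of Amendment 5, and in the production program.
2. Wherever the five-coefficient line is present, replace it with the form in Amendment 3: "estimate 'MenB06-ACWY' trtgrp 0 1 0 0 0 -1/ alpha=0.025 exp".
3. State that VE and its 97.5% CI for the 0,6 schedule are taken from that ESTIMATE output, and change the success data step to match. Adding the zero alone would leave the printed success flag unchanged.
4. Print the contrast coefficients (E option) for every schedule contrast, to confirm that ACWY is the reference.

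The cost is one added zero, a short edit to the data step, and a look at one page of output. No data collection, sample size or hypothesis changes.

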#### **5.3.2.4. Effectiveness (Responder-based): rMenB+OMV NZ - 2 doses (0,6-months schedule)**

Not applicable

#### **5.3.2.5. Vaccine effectiveness (Test-based): rMenB+OMV NZ - 2 doses (0,2-months schedule)**

See Section 5.3.2.1, with the difference the outcome data for group R is from one month after the 2nd vaccination instead of one month after the 3rd vaccination.

#### **5.3.2.6. Effectiveness (Responder-based): rMenB+OMV NZ - 2 doses (0,2-months schedule)**

Not applicable

#### **5.3.2.7. Lot-to-lot consistency: MenABCWY - ACWY component**

Not applicable

### 5.3.2.8. Immunological non-inferiority: MenABCWY vs. MenACWY

As a sensitivity analysis, a parametric model will be run. A generalized linear model with factors for vaccine group and randomization factors (i.e. region (US/ex-US), age category (10-17 YoA/18-25 YoA)) will be ran, with the Binary distribution and link function is identity, and outcome is 4-fold rise. If the lower limit of the two-sided 97.5% CI for the difference in percentage of subjects with 4-fold rise between the 2 groups (ABCWY (pooled) lots –ACWY) coming from the model is above -10%, also the sensitivity analysis has demonstrated non-inferiority. If the co-primary effectiveness objectives for rMenB+OMV NZ are met (Sections 5.3.1.1 through 5.3.1.6), then the above will be evaluated at 95% CI.

### 5.3.2.9. Vaccine effectiveness (Test-based): MenABCWY

See Section 5.3.2.1, with the difference in the estimate statement:

```
PROC GENMOD data=dataset descending;
class trtgrp strain region agecat previousACWY subject_id ;
model outcome = trtgrp strain region agecat previousACWY / dist= bin
link= log DSCALE ;
repeated subject = subject_id / type= CS withinsubject= strain ;
estimate 'MenABCWY-ACWY' trtgrp 0 0 1 1 1 -3/ alpha=0.025 exp
divisor=3;

/*trtgrp T, U, and V are the ABCWY-1, ABCWY-2, and ABCWY-3 lots and
trtgrp W is ACWY*/
run;
```

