## **6. ANALYSIS INTERPRETATION**

Multiple objectives and endpoints require type I error control. Full alpha (0.05) is split equally ( $\alpha=0.025$ ) between rMenB+OMV NZ objectives and MenABCWY objectives. Furthermore, within rMenB+OMV NZ, as well as within MenABCWY, objectives are tested hierarchically. If the first null hypothesis is rejected, then the testing will continue with the second hypothesis at same alpha. Same for 3rd, 4th, and so forth. Whenever a null hypothesis is not rejected, then the testing will stop.

As the comparator for MenABCWY non inferiority objective for the B component will be the selected schedule of rMenB+OMV NZ as determined in this study, the objectives of rMenB+OMV NZ will be analysed first. Additionally, if all null hypotheses related to rMenB+OMV NZ objectives will be rejected, the alpha ( $\alpha=0.025$ ) will be propagated to the MenABCWY part, and hypotheses related to MenABCWY objectives will be tested at full alpha ( $\alpha=0.05$ ). See Figure 2 for an explanation of the hierarchical testing (top to bottom, the order indicated by the arrows).

**Figure 2** Hierarchical testing of hypothesis

\* Alpha split equally between rMenB+OMV NZ and MenABCWY vaccine objectives.

If all rMenB+OMV NZ objectives achieved, MenABCWY vaccine objectives will be tested at full alpha.

\*\* If all objectives of rMenB+OMV NZ are met, the comparator will be the 0,2-months schedule. If the 0,2-months objective is not met, and the 0,6-months is met, then the 0,6-months schedule will be the comparator. If the 0,6-months is also not met, then the 0,2,6-months schedule will be the comparator.

Refer to Glossary of terms for definitions of test-based and responder-based vaccine effectiveness.

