
Vaccine effectiveness (Test-based): MenABCWY vaccine
 
To demonstrate the effectiveness of the MenABCWY vaccine against a randomly selected panel of endemic US N. meningitidis serogroup B invasive disease strains as measured by enc-hSBA at 1 month after the last MenABCWY vaccination (0,6-months) when compared to 1 month after the MenACWY vaccination.
 
Criterion:
 
LL of the two-sided 97.5% CIΔ for vaccine effectiveness is above 65% against a randomly selected strain panel between the ABCWY group (pooled lots) and the ACWY group.
	
The percentages of samples without bactericidal serum activity using enc-hSBA against each of the endemic US N. meningitidis serogroup B strains, at 1 month after the:
 
 
last vaccination for the ABCWY group (pooled) (Day 211, Month 7), and
 
1 month after the MenACWY vaccination in the ACWY group (Day 31, Month 1).
 

Effectiveness non-inferiority: MenABCWY vaccine vs. rMenB+OMV NZ vaccine
 
To demonstrate the non-inferiority of the effectiveness of the MenABCWY vaccine (0,6-months schedule) compared to the rMenB+OMV NZ vaccine (0,2,6-months or 0,6-months or 0,2-months)† in terms of percentage of samples with bactericidal serum activity using enc-hSBA against a randomly selected panel of endemic US N. meningitidis serogroup B invasive disease strains.
 
Criterion:
 
LL of the two-sided 97.5% CIΔ for the difference in percentages of samples with bactericidal serum activity using enc-hSBA against a randomly selected panel of
	
The percentages of samples with bactericidal serum activity using enc-hSBA against each of the endemic US N. meningitidis serogroup B strains at 1 month after the:
 
 
last MenABCWY vaccination (Day 211, Month 7) for the ABCWY group (pooled lots), and
 
3-dose vaccination series of rMenB+OMV vaccine (Day 211, Month 7 in MenB_0_2_6 group) or 2-dose vaccination series (Day 211, Month 7 in MenB_0_6 group) or 2-dose vaccination series (Day 91, Month 3 in MenB_0_2_6 group)†
 

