**CONFIDENTIAL**

205416 [MENB REC 2ND GEN-038 (V72\_72)]

Statistical Analysis Plan Amendment 4

Objectives	Endpoints
	
 
1 month after the single MenACWY vaccination in the ACWY group (Day 31, Month 1) as compared to baseline (Day 1, Month 0).
 
 
5. The total IgG as measured by ELISA GMCs against serogroups A, C, W and Y at baseline (Day 1, Month 0) and:
 
 
at 1 month after the first (Day 31, Month 1) and the last MenABCWY vaccination (Day 211, Month 7) for the ABCWY group (pooled lots), and
 
at 1 month after the MenACWY vaccination in the ACWY group (Day 31, Month 1).
 

Abbreviations: ELISA = enzyme-linked immunosorbent assay; Enc-hSBA = endogenous complement human serum bactericidal assay; GMC = geometric mean concentrations; GMT = geometric mean titre; GMR = geometric mean ratio; CI = confidence interval; hSBA = human serum bactericidal assay; LOD: limit of detection; LLOQ = lower limit of quantitation; LL = lower limit; AE = Adverse event; SAE = Serious adverse event; AESI = Adverse event of special interest

*N.meningitidis* serogroup B indicator strains = M14459, 96217, M07-0241084 and NZ98/254 for fHbp, NadA, NHBA and PorA P1.4 antigens, respectively. The NHBA indicator strain may be subject to change during the study, before clinical testing starts. In this case, this change will be documented either in a protocol amendment or in the clinical report.

Refer to Protocol Section 10 for details on evaluation of objectives and sample size justification. Refer to Glossary of terms for definitions of test-based and responder-based effectiveness

^ If the co-primary effectiveness objectives for rMenB+OMV NZ are met, then all objectives for MenABCWY will be evaluated at 95% CI. Refer to Protocol Section 10.1 for details

† If all objectives of rMenB+OMV NZ are met, the comparator will be the 0,2-months schedule. If the 0,2-months objective is not met, and the 0,6-months is met, then the 0,6-months schedule will be the comparator. If the 0,6-months is also not met, then the 0,2,6-months schedule will be the comparator.

\*For the Men A, C, W, Y evaluation, the 4-fold rise is defined as:

- a post-vaccination hSBA titre  $\geq 4$  times the LOD for subjects with a pre-vaccination hSBA titre  $< \text{LOD}$

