#### **5.3.1.9. Vaccine effectiveness (Test-based): MenABCWY**

See Section 5.3.1.1. If the co-primary effectiveness objectives for rMenB+OMV NZ are met (Sections 5.3.1.1 through 5.3.1.6), then the VE for MenABCWY will be evaluated at 95% CI.

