### 5.3.2.10. Effectiveness non-inferiority: MenABCWY vs. rMenB+OMV NZ

As a sensitivity analysis, a parametric model will be run. A generalized linear model with factors for vaccine group and randomization factors (i.e. region (US/ex-US), age category (10-17 YoA/18-25 YoA), previous MenACWY vaccination (y/n)) will be ran, with the Binary distribution and link function is identity, and outcome is bactericidal activity measured by enc-hSBA at 1:4 dilution. If the lower limit of the two-sided 97.5% CI for the difference in percentage of samples with bactericidal activity measured by enc-hSBA at 1:4 dilution between the 2 groups (ABCWY (pooled) lots –MenB) coming from the model is above -5%, also the sensitivity analysis has demonstrated non-inferiority. If the co-primary effectiveness objectives for rMenB+OMV NZ are met (Sections 5.3.1.1 through 5.3.1.6), then the above will be evaluated at 95% CI.

In addition to the comparison of MenABCWY vs the selected MenB schedule per Section 5.3.1.10, MenABCWY will be compared to the other MenB schedule/schedules, whichever is applicable in the same way as described in Section 5.3.1.10. If MenB 0,2 schedule is selected as comparator, in addition MenABCWY will be compared to Menb 0,6 and MenB 0,2,6 schedule. If MenB 0,6 schedule is selected as comparator, in addition MenABCWY will be compared to MenB 0,2,6 schedule. No success criterion is defined for these group comparisons.

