## **6. ANALYSIS INTERPRETATION**

Multiple objectives and endpoints require type I error control. Full alpha (0.05) is split equally ( $\alpha=0.025$ ) between rMenB+OMV NZ objectives and MenABCWY objectives. Furthermore, within rMenB+OMV NZ, as well as within MenABCWY, objectives are tested hierarchically. If the first null hypothesis is rejected, then the testing will continue with the second hypothesis at same alpha. Same for 3rd, 4th, and so forth. Whenever a null hypothesis is not rejected, then the testing will stop.

As the comparator for MenABCWY non inferiority objective for the B component will be the selected schedule of rMenB+OMV NZ as determined in this study, the objectives of rMenB+OMV NZ will be analysed first. Additionally, if all null hypotheses related to rMenB+OMV NZ objectives will be rejected, the alpha ( $\alpha=0.025$ ) will be propagated to the MenABCWY part, and hypotheses related to MenABCWY objectives will be tested at full alpha ( $\alpha=0.05$ ). See Figure 2 for an explanation of the hierarchical testing (top to bottom, the order indicated by the arrows).

**Figure 2** Hierarchical testing of hypothesis

\* Alpha split equally between rMenB+OMV NZ and MenABCWY vaccine objectives.

If all rMenB+OMV NZ objectives achieved, MenABCWY vaccine objectives will be tested at full alpha.

\*\* If all objectives of rMenB+OMV NZ are met, the comparator will be the 0,2-months schedule. If the 0,2-months objective is not met, and the 0,6-months is met, then the 0,6-months schedule will be the comparator. If the 0,6-months is also not met, then the 0,2,6-months schedule will be the comparator.

Refer to Glossary of terms for definitions of test-based and responder-based vaccine effectiveness.

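### The SAP code for the pooled MenABCWY VE contrast fixes alpha at 0.025, although the plan calls for a 95% CI once all rMenB+OMV NZ objectives are met (minor)

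*SAP*

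**What the plan says.** - **Overall rule (SAP Section 6, Amendment 4; same in Amendment 5).** "Full alpha (0.05) is split equally" between the rMenB+OMV NZ and MenABCWY families, 0.025 each. If all rMenB+OMV NZ null hypotheses are rejected, "hypotheses related to MenABCWY objectives will be tested at full alpha", that is 0.05.
- **Table 1 footnote (Amendment 4).** "If the co-primary effectiveness objectives for rMenB+OMV NZ are met, then all objectives for MenABCWY will be evaluated at 95% CI".
- **Table 1 criterion for this objective.** The lower limit of the two-sided 97.5% CI, subject to that footnote, "for vaccine effectiveness is above 65% against a randomly selected strain panel between the ABCWY group (pooled lots) and the ACWY group".
- **Section 5.3.1.9, on this same objective.** If 5.3.1.1 to 5.3.1.6 are met, "then the VE for MenABCWY will be evaluated at 95% CI".
- **Section 5.3.2.9, the code for it.** "See Section 5.3.2.1, with the difference in the estimate statement", followed by a GENMOD block containing "estimate 'MenABCWY-ACWY' trtgrp 0 0 1 1 1 -3/ alpha=0.025 exp" and a divisor of 3. Nothing in the section mentions 95%.
- **Section 5.3.2.1, to which 5.3.2.9 refers.** It presents its code as what will be used for the VE calculation and describes the deciding limit at the 97.5% level, for the rMenB+OMV NZ three-dose objective.
- **Sections 5.3.2.8 and 5.3.2.10, either side of 5.3.2.9.** Each ends with the switch: "then the above will be evaluated at 95% CI" if the rMenB+OMV NZ objectives are met.

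**The concern.** For one primary objective, the text makes the CI level depend on the rMenB+OMV NZ results, while the prescribed code has a single fixed level. The two agree when alpha stays at 0.025. They disagree when alpha is passed on, which is the case the propagation rule was written for. A programmer who follows 5.3.2.9 literally would then report a 97.5% interval for a test that the plan assigns to a 95% interval.

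The history suggests an oversight. In Amendment 1, 5.3.1.9 had no 95% sentence. From Amendment 2 the sentence stands in 5.3.1.9, 5.3.2.8 and 5.3.2.10, and the 5.3.2.9 block was rewritten with alpha moved from the MODEL to the ESTIMATE statement, but no switch was added there. At stake is some power on a primary objective, and a reported interval that does not match the plan's own rule.

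**Working it through.** **Inputs**
- Full alpha 0.05, split equally (Section 6).
- Coded alpha 0.025 two-sided (5.3.2.9).
- Level after propagation: 95% CI, alpha 0.05 two-sided (5.3.1.9, Table 1 footnote, Section 6).
- Success: lower VE limit above 65%, which is an upper RR limit below 0.35 (Table 1).
- SE of log RR: not given in the SAP, so assumed over 0.02 to 0.15.

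**1. The plan's own levels.** 0.05 / 2 = 0.025, giving a 97.5% CI before propagation; 0.025 + 0.025 = 0.05, giving a 95% CI after it. These reproduce.

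**2. Critical values.** Alpha 0.025 two-sided gives z = 2.2414; alpha 0.05 gives z = 1.9600. The ratio is 2.2414 / 1.9600 = 1.144, so the coded interval on the log RR scale is about 14% wider. The one-sided level is 0.0125 instead of 0.025.

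**3. Power.** For a test with a given power at the 95% CI, power at the 97.5% CI is Phi(1.960 + z_power − 2.241).

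| Power at intended 95% CI | Power at coded 97.5% CI |
|---|---|
| 80% | 71% |
| 90% | 84% |
| 95% | 91% |

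**4. Smallest observed VE that passes.** Success requires log(RR) + z × SE < log(0.35), so the threshold is VE = 100 × (1 − 0.35 × exp(−z × SE)).

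| Assumed SE of log RR | 95% CI (text) | 97.5% CI (code) | Window, about |
|---|---|---|---|
| 0.02 | 66.35% | 66.53% | 0.2 points |
| 0.05 | 68.27% | 68.71% | 0.4 points |
| 0.10 | 71.23% | 72.03% | 0.8 points |
| 0.15 | 73.92% | 74.99% | 1.1 points |

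Example: with SE 0.05 and an observed VE of 68.49%, the lower limit is 65.25% at the 95% level (met) and 64.75% at the 97.5% level (not met).

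**5. Which output carries the interval.** The success step printed in 5.3.2.1 takes its upper limit from the GEE parameter-estimate table, filtered to one treatment level. The alpha on the ESTIMATE statement does not set that limit, and a single treatment-level parameter cannot be the average of three lots against ACWY. In the printed program only the ESTIMATE line yields the pooled MenABCWY interval. Steps 2 to 4 therefore describe that interval, not the printed success flag.

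**The case against.** The strongest reply is that the plan already settles the level. Section 5.3.1.9 is the analysis section for this objective and gives the rule plainly; the Table 1 footnote and Section 6 agree; no prose assigns 97.5% to MenABCWY VE after propagation. The SAP also tends to show the default 97.5% level and put the 95% override in a separate sentence, so the code can be read as showing the default. Sections 5.3.2.8 and 5.3.2.10 define sensitivity models with their own criteria and so need their own sentence, whereas 5.3.2.9 only supplies code for 5.3.1.9.

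Much of this stands. The intended level is clear, which limits the point to a code correction. It does not remove the point, because 5.3.2.1 says its code will be used, 5.3.2.9 inherits that status, and the printed alpha is wrong in the propagated case.

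Three stronger readings are tempting and are not supported:
- *That the level could be chosen after seeing the data.* The trigger is pre-specified, the rMenB+OMV NZ objectives are analysed first, and 5.3.1.9 states which level follows.
- *That a borderline result literally fails under the code.* The printed success flag does not read the ESTIMATE output (working, step 5).
- *That a failure here would close later MenABCWY objectives.* Section 6 does stop testing at the first non-rejection, but what follows this objective depends on the order in Figure 2, which is not shown.

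**Conclusion.** The mismatch is real and minor. In Amendment 4, and identically in Amendments 2 and 3, the prescribed ESTIMATE statement matches the plan only if the rMenB+OMV NZ objectives are not all met. If they are, it gives an interval about 14% wider than allotted. The error is on the conservative side, so type I error is not at risk; the cost is the power loss in step 3 and a decision that differs only inside the narrow window in step 4.

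The window rests on assumed SEs and a Wald interval on the log RR scale; the power figures rest on the same normal approximation. The conclusion cannot be extended to the Amendment 5 code, because that version of 5.3.2.9 is in the part of the SAP not at hand. Its Section 6 keeps the propagation rule, so the check is needed.

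**What to change.** First check 5.3.2.9 in Amendment 5. If the fixed alpha is still there:
1. Replace `alpha=0.025` in the ESTIMATE statement with a parameter set by the gate: 0.05 if 5.3.1.1 to 5.3.1.6 are all met, 0.025 otherwise.
2. Take the deciding lower VE limit for this objective from the ESTIMATE output at that level, not from the GEE parameter table.
3. Add the 95% CI sentence already used in 5.3.2.8 and 5.3.2.10.

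The cost is one macro variable, one change of output source and one sentence. No extra data are needed.
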